**5.6. DATA COLLECTION TECHNIQUES**

Samples will be processed at the central laboratory of INCICH. Commercial reagents will be used for the determination of soluble inflammatory mediators, with the technique (enzyme-linked immunoassay or luminex platform) selected based on availability and accessibility. Mediators to be measured include leptin, TNF- $\alpha$ , IL-6, and CRP.

**5.7. SAMPLE PROCESSING**

Peripheral venous blood (4 mL) will be collected in a tube with activator gel, which will be centrifuged at 600 g for 15 minutes at 4°C. The serum obtained will be stored in aliquots of 500 µL at -70°C until analysis.

**STATISTICAL ANALYSIS PLAN**

Spreadsheet databases will be created using the Excel program. The Kolmogorov-Smirnov test will be used to assess variable distribution. Proportions and percentages will be used to describe dichotomous, nominal, and ordinal variables, while means with standard deviation or medians with interquartile ranges will be used to describe dimensional variables, depending on the type of distribution.

To compare differences between two independent groups, appropriate statistical tests (Fisher's exact test or chi-square test for discrete variables, Student's t-test or Mann-Whitney test for continuous variables) will be used. For dependent variables, the paired T-test or the Wilcoxon rank sum will be used. If analysis of 3 or more groups is required, the Kruskal-Wallis test or one-way ANOVA will be used.

Associations will be explored using Spearman or Pearson's rho coefficients, as appropriate. All analyses will be conducted using two-sided testing, with significance set at P < 0.05.

For statistical analysis, the GraphPad Prism version 6.0 (GraphPad Inc., San Diego, CA) and IBM SPSS Statistics program for macOS, version 25 (IBM, Armonk, NY) will be used.

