**PROJECT OBJECTIVES:**

**Primary(s):**

**Secondary(s):**

To determine the decrease in rheumatoid arthritis (RA) activity associated with plant-based diet modifications

- To analyze the factors associated with changes in disease activity.
- To evaluate changes in acute phase reactants.
- To identify the adipokines related to the decrease or increase in disease activity tumor necrosis factor-alpha (TNF- $\alpha$ ), Interleukin 6 (IL-6), Leptin, and C-reactive protein (CRP).

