5.3.5. Elimination criteria

- Patients who have died in the process before finishing the sampling.
- Patients who have suspended the intervention
- Lack of adherence to diet  $< 80\%$
- Loss to follow-up
- COVID infection requiring hospitalization (moderate-severe)

5.4. SAMPLE SIZE.

Convenience sampling will be carried out on patients at the National Institute of Cardiology who agree to participate, with a total n of 28.

5.5. SPECIFICATION OF DEPENDENT AND INDEPENDENT VARIABLE (S).

Variable	Measurement Level	Concept
DAS28 initial and post intervention	Continuous quantitative	Remission: <or equal to 2.6 (assess valid only in post-intervention), mild:> 2.6- <3.2, moderate:> or equal to 3.2- <or = 5.1, severe:> 5.1
CDAlinitial and post intervention	Continuous quantitative	<or equal 2.8, remission,> 2.8-10: mild activity, moderate> 10-22: moderate activity,> 22 serious activity
SDAI initial and post intervention	Continuous quantitative	<or equal to 3.3: remission, 3.3-11 mild activity,> 11-26 moderate activity,> 26 serious activity
PCR	Continuous quantitative	
Globular Sedimentation Volume (GSV)	Continuous quantitative	
IL-6	Continuous quantitative	
Adiponectin	Continuous quantitative	Protein produced mainly by adipocytes that belongs to the adipokine family.
Aggregate comorbidities (DM, HAS, Hypothyroidism, Dandslipidemia, smoking)	Nominal qualitativ.	Concomitant diseases added to patients, determined as present or not.
Age of diagnosis	Discrete quantitative.	Determined in completed years
Age of the patient	Discrete quantitative.	Determined in completed years
Gender	Nominal qualitativ.	Dichotomous in feminine or masculine
BMI	Continuous quantitative	Determination estimated according to weight and height, standardized by degrees in overweight (25-29.9), obesity grade I (30-34.9), grade II (35-40) and morbid obesity (> 40)
% total body fat	Continuous quantitative	Measurement established by bioimpedance determined by weighing machine TANITA
% visceral fat	Continuous quantitative	Measurement established by bioimpedance determined by weighing machine TANITA
% muscle / water	Continuous quantitative	Measurement established by bioimpedance determined by weighing machine TANITA
Morning stiffness	Nominal qualitativ.	Patient's perception of gelling phenomenon that improves with physical activity over a period of time.

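### A Kolmogorov-Smirnov check steers the summaries and, by natural reading, the tests, with only raw-scale options; if the mediators are lognormal this costs about 6 to 18 points of power, mostly through not taking logs

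*Protocol*

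**What the plan says.** The protocol's Statistical Analysis Plan section opens with the distribution check: "The Kolmogorov-Smirnov test will be used to assess variable distribution". Continuous variables are then summarised by mean and SD or by median and interquartile range, "depending on the type of distribution". For before-after comparisons it says: "For dependent variables, the paired T-test or the Wilcoxon rank sum will be used". No sentence states what decides between those two tests. The distribution check is the only criterion the section offers, so choosing the test by it is the natural reading, but an inferred one.

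The section does not say whether the Kolmogorov-Smirnov test is run with the Lilliefors correction, or whether it is applied to initial values, post-intervention values or within-patient differences. It mentions no transformation. The error rate is fixed: "All analyses will be conducted using two-sided testing, with significance set at P < 0.05".

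Section 5.4 sets a convenience sample "with a total n of 28", without a power calculation. Section 5.6 lists leptin, TNF-alpha, IL-6 and CRP as the mediators; the variable table in section 5.5 adds adiponectin. Acute-phase reactants and adipokines are two of the three secondary objectives. The primary objective is disease activity.

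**The concern.** A normality test at 28 patients is a weak guide to the scale of analysis. Not rejecting is easily taken as evidence of normality, and a skewed concentration then goes to a raw-scale paired t-test, where a few high values dominate the change. When the check does reject, the alternative is a rank test on the same raw scale. Neither route uses the log scale, which is the obvious candidate for concentrations if they are right-skewed.

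The routing is also ambiguous. A paired t-test depends on the distribution of the differences, whereas the text tests the variable, and a variable measured twice can receive two verdicts. At stake are power and a clear effect estimate for the secondary laboratory outcomes.

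**Working it through.** **Inputs from the protocol.** n = 28 (section 5.4); two-sided 5% level, Kolmogorov-Smirnov check, paired t or Wilcoxon (Statistical Analysis Plan section). There is no power figure to reproduce.

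**Assumptions, not in the protocol.** Mediators lognormal; multiplicative change; log-SD σ of 0.5, 0.8 or 1.0 with true post/initial ratio 0.80, 0.70 or 0.65; within-patient log correlation ρ = 0.7.

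**Step 1: what the check detects.** By simulation at n = 28, the 5% critical value of the statistic D is 0.164 with Lilliefors and 0.250 uncorrected. With mean and SD estimated from the data, the uncorrected version has a true size of about 0.01%. Detection of skew in initial values:

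| log-SD | Lilliefors | uncorrected |
|---|---|---|
| 0.3 | 21% | 0% |
| 0.5 | about 45% | 3% |
| 0.8 | 80% | 20% |
| 1.0 | about 91% | 38% |

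With Lilliefors, initial and post values of the same mediator get opposite verdicts in 43% of trials at log-SD 0.5 and 29% at 0.8. The raw-scale paired t and signed-rank tests disagree on significance in 8%, 15% and 22% of trials at log-SD 0.5, 0.8 and 1.0.

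**Step 2: power of a fixed log-scale paired t-test.** SD of the log difference = σ√(2(1 − ρ)); standardised change d = |ln ratio| / that SD; noncentrality = d√28, on 27 degrees of freedom.

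- σ = 0.5: SD = 0.5 × √0.6 = 0.387; d = 0.223/0.387 = 0.576; noncentrality 3.05; power 83.6%.
- σ = 0.8: SD = 0.620; d = 0.357/0.620 = 0.576; noncentrality 3.05; power 83.5%.
- σ = 1.0: SD = 0.775; d = 0.431/0.775 = 0.556; noncentrality 2.94; power 81.0%.

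**Step 3: power of the other routes (10,000 trials each).** The pretest route uses signed-rank if the check rejects and raw-scale paired t otherwise. The fixed signed-rank column has no pretest, so it separates the two sources of loss.

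| σ / ratio | log paired t | fixed raw signed-rank | pretest, Lilliefors | pretest, uncorrected |
|---|---|---|---|---|
| 0.5 / 0.80 | 83.8% | 78.5% | 77.2-77.7% | 76% |
| 0.8 / 0.70 | 83.2% | 75.1% | 73.2-73.8% | 68% |
| 1.0 / 0.65 | 80.5% | 70.6% | 69.4-69.6% | 62% |

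- Total loss, smallest: 83.8 − 77.7 = 6.1 points. Largest: 80.5 − 62 = 18.5; a repeat run in whole percentages gave 81 − 63 = 18.
- Loss from not taking logs: 83.8 − 78.5 = 5.3; 83.2 − 75.1 = 8.1; 80.5 − 70.6 = 9.9.
- Loss from the pretest, Lilliefors: 78.5 − 77.7 = 0.8 up to 75.1 − 73.2 = 1.9.
- Loss from the pretest, uncorrected: 78.5 − 76 = 2.5; 75.1 − 68 = 7.1; 70.6 − 62 = 8.6 (repeat run 71 − 63 = 8).

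**Step 4: other models.**

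- Additive raw-scale change on a skewed baseline: log t 80-84%, pretest 78-80%, a loss of 0 to 5 points.
- Near-normal DAS28 (assumed mean 4.5, SD 1): paired t 80%, pretest 80%, no loss.
- No true change: type I error of the pretest route is 4.1-5.3%.
- Heavy-tailed log changes (t with 3 degrees of freedom, log-SD 0.5): log t 66.5%, fixed signed-rank 65.1%, Lilliefors pretest 49.7% (on initial values) or 61.6% (on differences). Here the pretest is the main cause, so the split in Step 3 belongs to the lognormal model.

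**The case against.** The best defence is that the pretest is blamed for a loss it mostly does not cause. Under the lognormal model a signed-rank test fixed in advance, with no pretest at all, already gives up 5 to 10 points; deleting the pretest alone would recover little. This stands, and it is why the fix must set the scale as well.

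The comparison also favours the log-scale test by construction, since lognormal data with a multiplicative change are its ideal case, and the protocol gives no distribution, SD, correlation or expected change. This stands too: the range is conditional. The upper end further requires an uncorrected check, which the protocol neither states nor excludes.

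The protocol ties the check in words only to the summary statistics, and the link to the tests is inferred. That is right, though no other criterion is offered.

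Finally, it can be said that fixing a scale for each mediator is detail for a separate SAP. This carries less weight. The protocol has its own section under that title, and that section states a data-driven rule and names the available tests, so the point concerns what is written.

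**Conclusion.** The point holds as a modest weakness in the analysis of the secondary laboratory outcomes. The plan pairs a weak distribution check with raw-scale methods only. Under the lognormal assumptions above, the combination costs about 6 to 18 points of power against a fixed log-scale paired t-test. Most of that comes from the scale; the pretest adds about 1 to 2 points with Lilliefors and about 2 to 8 uncorrected.

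A reader might infer three stronger things that the material does not support:

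- That the pretest by itself costs 6 to 18 points. It does not under this model, and no such figure can be derived from the protocol alone.
- That skew in general goes undetected. With Lilliefors, strong skew is found about nine times in ten; the gap is in mild to moderate skew.
- That the primary result is compromised, or that choosing the test after seeing the data inflates false positives. Type I error stays near 5%, and a near-normal DAS28 loses no power.

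**What to change.** Rewrite the relevant sentences of the Statistical Analysis Plan section so that the method is fixed per variable:

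- Stop using the normality check to select tests. If one is kept, apply it to the within-patient differences, for description only.
- Change in DAS28, CDAI and SDAI: paired t-test with 95% CI.
- CRP, ESR and the mediators: paired t-test on the log scale, reported as the post/initial geometric mean ratio with 95% CI.
- Sensitivity analysis for all of these: Wilcoxon signed-rank test. The rank sum test that the section now names for dependent data is for independent samples and should be replaced.

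The cost is a paragraph of wording; no data collection changes. There are two small downsides: values below an assay limit need a substitution rule before logs are taken, and mediator effects are reported as ratios, not differences.

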Based on this evidence, this study aims to determine the decrease in RA activity associated with modifications of the plant-based diet. To carry out this protocol, we will evaluate women and men who are 18 years old or older with low, moderate, or severe RA activity. For the dietary intervention, at the beginning of the treatment, the RA patients will be evaluated anthropometrically (weight, height, body mass index, waist and hip circumference, waist-hip index, percentage of total fat, visceral fat, and percentage of muscle) and will have a baseline blood sample taken. The kilocalories consumed regularly will be calculated through a 24-hour recall to establish their personalized meal plan. A diet synthesis table will be created with the following macronutrient distribution: carbohydrates 57%, protein 18%, and lipids 25%. Subsequently, a distribution of the food will be made in an equivalent distribution table, complying with the kilocalories and the established percentage of macronutrients. The consumption of animal-origin foods will be reduced, replacing this protein with protein of vegetable origin. The intervention will be carried out for 15 days, and the menu will be modified after seven days of intervention following the same specifications.

At the end of the treatment, the patients will be evaluated under the same anthropometric conditions, and a blood sample will be collected for laboratory analysis. The DAS (Disease Activity Score) index, a scale that measures RA activity, will be used to determine the severity of the pathology. This scale takes into account the count of swollen and painful joints over 28 joints, the erythrocyte sedimentation rate (ESR), and the evaluation of the disease by the patient. The scale has a rating of 0.0 to 9.4.

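### The plan names the Wilcoxon rank sum, an independent-samples test, for the paired before/after comparison; the signed-rank test is needed

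*Protocol*

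**What the plan says.** The Statistical Analysis Plan section of the protocol deals with two situations in consecutive sentences. The first begins "To compare differences between two independent groups" and, for continuous outcomes, gives "Student's t-test or Mann-Whitney test for continuous variables". The second reads "For dependent variables, the paired T-test or the Wilcoxon rank sum will be used". The section also sets the error rate: "All analyses will be conducted using two-sided testing, with significance set at P < 0.05".

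The second sentence governs the main comparison. The aim under Project Objectives is "To determine the decrease in rheumatoid arthritis (RA) activity associated with plant-based diet modifications". The Abstract describes re-evaluation of the same patients: "At the end of the treatment, the patients will be evaluated under the same anthropometric conditions". The variable table in section 5.5 lists "DAS28 initial and post intervention", and CDAI and SDAI likewise. Section 5.2 calls the design longitudinal, and no comparator arm is described. Section 5.4 gives the sample as "with a total n of 28", chosen by convenience. The signed-rank test is not named anywhere in the protocol.

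**The concern.** The Wilcoxon rank-sum test and the Mann-Whitney test are one procedure under two names. Both compare two independent samples. The section therefore assigns a single independent-samples test to independent data under one name and to dependent data under the other. The non-parametric counterpart of the paired t-test is the Wilcoxon signed-rank test.

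A one-group before/after design gains its precision from comparing each patient with himself or herself. A rank-sum test on the 28 before and 28 after values treats them as 56 unrelated observations and gives up that gain. When the two values in a patient are positively correlated, the test overstates the variability of the change, rejects too rarely, and can miss a real small-to-moderate improvement. An analyst who instead runs the correct signed-rank test departs from the written plan.

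**Working it through.** **Inputs from the protocol.** 28 patients (section 5.4); two-sided 0.05 (Statistical Analysis Plan); two measurements per patient (Abstract, section 5.5). The protocol states no power, SD, correlation or expected change, so there is no figure of its own to reproduce.

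**Assumed.** Bivariate normal values with SD 1 at each visit, and correlation ρ between visits over a range. A log-normal version (log-SD 1) stands in for skewed markers. All figures take 28 analysed pairs.

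**Step 1: are the two names one test?** On one simulated data set the rank-sum and the Mann-Whitney (asymptotic, no continuity correction) both gave p = 0.3175. The signed-rank test gave p = 0.1638. They are the same test, and the signed-rank is a different one.

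**Step 2: why ignoring the pairing is conservative.** The analogy with means shows the direction. The true variance of the mean change is 2σ²(1−ρ)/n, but an independent-samples test assumes 2σ²/n. Its standardised statistic is therefore too small by a factor √(1−ρ), and the real two-sided type I error is about 2[1−Φ(1.96/√(1−ρ))]. At ρ = 0.5 this is 2[1−Φ(1.96/0.707)] = 2[1−Φ(2.77)] ≈ 0.6%, where 5% was intended.

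**Step 3: simulation of the tests themselves.** 20,000 trials of 28 pairs per scenario; entries are rank-sum / signed-rank, as percentages. For type I error the signed-rank test stayed between 4.4% and 4.8%.

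| ρ | Rank-sum type I error | Power, change 0.5 SD | Power, change 0.8 SD |
|---|---|---|---|
| 0.3 | 1.8 | 41 / 55 | 85 / 92 |
| 0.5 | 0.8 | 40 / 69 | 89 / 98 |
| 0.7 | 0.1 | 39 / 89 | 93 / 99.9 |

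At ρ = 0 the rank-sum type I error is 4.6%. At a change of 1.0 SD the loss of power is at most about 2 points. A separate run of 10,000 trials gave 41 / 55, 41 / 70 and 39 / 89 for the 0.5 SD column.

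**Step 4: change fixed in SDs of the differences.** The change is set at 0.55 SD of the within-patient differences, for which the paired t-test has 80% power. On the raw scale this is 0.55·√(2(1−ρ)): 0.65 SD at ρ = 0.3, 0.55 at 0.5, 0.43 at 0.7 and 0.35 at 0.8.

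| ρ | Normal: rank-sum / signed-rank | Log-normal, same shift on the log scale |
|---|---|---|
| 0 | 79 / 78 | 79 / 73 |
| 0.3 | 67 / 78 | 66 / 71 |
| 0.5 | 50 / 78 | 51 / 71 |
| 0.7 | 24 / 78 | 23 / 70 |
| 0.8 | 9 / 78 | 9 / 69 |

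Part of the fall down the rank-sum columns comes from the raw change shrinking as ρ rises. Step 3, with the raw change fixed, is the plainer comparison.

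**The case against.** The strongest reply is that this is a naming slip with a clear intent. The sentence opens by referring to dependent data and places the term beside the paired t-test, so most analysts would choose the related-samples procedure. That is likely, and it is why the point is minor. It does not make the text right: the test named is a real and different one, in the protocol's only stated rule for the main comparison.

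A second reply is that the rank test would seldom be used on normal data. The section checks distributions with Kolmogorov-Smirnov. If that check selects the test (the section ties it explicitly only to the descriptive statistics), normal data lead to the rank option in only about 10% of trials. For a 0.5 SD change, the power of the whole procedure is then 56%, 69% and 86% at correlations 0.3, 0.5 and 0.7, close to the signed-rank figures. This stands: the normal-data figures are the cost when the rank option is used, not the expected loss over the whole plan. For the log-normal data the same check selects the rank option about 98–99% of the time, and the loss is then the one in the last column of Step 4. That case may suit skewed inflammatory markers; nothing in the protocol shows that DAS28 behaves so.

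Third, section 5.3.5 removes patients for poor adherence, suspension of the intervention or loss to follow-up, and the text does not say whether 28 is counted before or after this. The figures therefore assume 28 complete pairs. Finally, basing the test choice on the differences is a detail that a separate analysis plan could hold. It is included in the fix because it belongs to the same sentence and costs nothing more.

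**Conclusion.** The concern holds. The protocol prescribes an independent-samples test for paired data, and this reaches the main before/after comparison whenever the non-parametric option is taken. The error in naming is certain from the text. The size of the consequence depends on assumptions that the protocol does not supply: for 28 pairs and a change of 0.5 SD, the loss is about 14 points of power at correlation 0.3 (55 − 41), 29 at 0.5 (69 − 40) and 50 at 0.7 (89 − 39). There is no loss at zero correlation and very little at a change of 1 SD. Under positive correlation the error runs in the conservative direction and does not raise the risk of a false claim of benefit. Because a slip is likely and the correction is simple, the severity is minor.

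**What to change.** In the Statistical Analysis Plan section, replace the rank-sum test in the sentence on dependent data with the Wilcoxon signed-rank test on the within-patient differences (post minus initial). In the same sentence, state that the choice between it and the paired t-test rests on the distribution of those differences, since that is what the paired t-test assumes about. The sentence on independent groups can stay as it is. The cost is one phrase of text, with no extra data or patients.

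### Must the search for factors associated with DAS28 change be adjusted for initial DAS28 and stripped of the score's components?

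*Protocol*

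**What the plan says.** The first secondary objective in the Protocol's Project Objectives is "To analyze the factors associated with changes in disease activity". The second concerns acute phase reactants. The third relates TNF-alpha, IL-6, leptin and CRP to the rise or fall of disease activity.

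The Protocol's Statistical Analysis Plan gives bivariate methods only. For associations, "Associations will be explored using Spearman or Pearson's rho coefficients, as appropriate". For categorical variables it has tests introduced by "To compare differences between two independent groups, appropriate statistical tests", and "If analysis of 3 or more groups is required, the Kruskal-Wallis test or one-way ANOVA will be used". It adds: "All analyses will be conducted using two-sided testing, with significance set at P < 0.05". It mentions no regression, partial correlation or analysis of covariance.

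Section 5.4 describes a convenience sample of patients "who agree to participate, with a total n of 28". Section 5.5 is headed as a list of dependent and independent variables but does not say which is which. It contains DAS28 before and after the intervention, the sedimentation rate (as globular sedimentation volume), and the swollen and painful joint counts. It also lists age, age at diagnosis, gender, BMI, body composition, comorbidities and baseline treatment. The Abstract describes DAS28 as built from the two joint counts, the sedimentation rate and the patient's own evaluation, so three of its four components are in the list.

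**The concern.** Two artefacts are possible. First, change is the post value minus the initial value, so it is negatively correlated with the initial value even when nothing has happened. A factor that shares the chance part of the initial value picks up some of that correlation. Second, correlating DAS28 change with a joint count or the sedimentation rate correlates a total with one of its parts.

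If either were reported as a finding, the trial could present severe initial disease, or a marker of it, as predicting response to the diet when the result reflects re-measurement only. The apparent remedy is cheap: regress post-intervention DAS28 on initial DAS28 plus the factor, and drop the components from the candidates. The data are already collected and the cost is one degree of freedom per model.

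**Working it through.** **Inputs.** From the Protocol: n = 28, two-sided 5% level. Assumed, because the Protocol gives no figure: pre-post correlation r of DAS28 (0.5 to 0.9), equal variances at the two visits, and correlation q between a factor and initial DAS28 (0.3 to 0.6). The plan states no figure of its own to reproduce.

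**Step 1. Critical values.** For a raw correlation, t(0.975; 26) = 2.056 and 2.056/√(26 + 2.056²) = 0.374. For a correlation adjusted for one covariate, t(0.975; 25) = 2.060 and 2.060/√(25 + 2.060²) = 0.381.

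**Step 2. Initial DAS28 against change, no effect.** The expected correlation is −√((1 − r)/2). At r = 0.7 this is −√0.15 = −0.39. In 20,000 simulated trials per setting:

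| r | expected correlation | significant (Pearson) | significant (Spearman) |
|---|---|---|---|
| 0.5 | −0.50 | 81% | 74% |
| 0.6 | −0.45 | 68% | 62% |
| 0.7 | −0.39 | 54% | 49% |
| 0.8 | −0.32 | 38% | 34% |
| 0.9 | −0.22 | 21% | 19% |

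The artefact is real if that correlation is computed and read as prediction.

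**Step 3. Another factor, two null models.** The factors are not randomised, so the result depends on why a factor correlates with initial DAS28.

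*Model A: the factor tracks the observed initial value, error included, and is unrelated to the post value given it.* Its correlation with change is −q√((1 − r)/2); at q = 0.6 and r = 0.7, −0.6 × 0.387 = −0.23. Its adjusted correlation is 0.

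*Model B: the factor tracks stable severity, and each visit adds independent error.* Change is then the difference of two errors, so the factor's correlation with change is 0. The factor correlates q with both visits, so its correlation with post DAS28 given initial DAS28 is q(1 − r)/√((1 − q²)(1 − r²)) = [q/√(1 − q²)] × √((1 − r)/(1 + r)). At q = 0.6 and r = 0.5 this is 0.75 × 0.577 = 0.43, above the critical 0.381. At r = 0.8 it is 0.75 × 0.333 = 0.25.

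Share of null trials called significant, n = 28, q = 0.6:

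| r | A: raw | A: adjusted | B: raw | B: adjusted |
|---|---|---|---|---|
| 0.5 | 35% | 5% | 5% | 64% |
| 0.6 | 29% | 5% | 5% | 50% |
| 0.7 | 23% | 5% | 5% | 36% |
| 0.8 | 16% | 5% | 5% | 24% |

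For q from 0.3 to 0.5 and r from 0.5 to 0.8, the raw correlation under A gives about 8% to 25%, and the adjusted model under B gives about 8% to 40%. Each method is valid under one model and fails under the other.

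**Step 4. Components.** Suppose a component's change is correlated with DAS28 change and the component is unrelated to the rest of the score. It is significant in 39% to 97% of trials for assumed variance shares of 0.10 to 0.40. A component's baseline value against DAS28 change gives 10% to 31% (shares 0.15 to 0.40, r 0.6 to 0.8). Baseline adjustment does not cure this part-whole link; only leaving the components out does.

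**Step 5. Does the plan ask for these correlations?** Section 5.5 assigns no roles. The joint counts are needed to compute DAS28, and the sedimentation rate can serve the separate objective on acute phase reactants. No sentence names them, or initial DAS28, as candidate factors. TNF-alpha, IL-6, leptin and CRP are not components of DAS28 as the Abstract describes it, so the part-whole argument does not reach the third objective.

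**The case for a change.** The strongest case for a change is that the Protocol has a section headed as its statistical analysis plan, and that section does fix methods, none of them adjusted. Nothing keeps initial DAS28 or its components out of the candidates. The significance level is applied to every analysis, which weakens the reading that associations are merely explored. Nor does the artefact need initial DAS28 itself as a factor: under Model A, any marker of initial severity inherits it. The entry rule of DAS28 above 2.6 does not remove it either. With the initial value truncated 1.0 or 1.5 SD below its mean (assumed), initial DAS28 against change is still significant in 26% to 70% of null trials for r 0.8 to 0.5.

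The arithmetic stands, and so does the observation that the candidate factors are unnamed. The step to a required adjustment does not. It takes Model A for granted, whereas age, age at diagnosis, BMI, comorbidities and treatment could as plausibly follow a patient's lasting severity (Model B). For those, the adjusted model would create the false associations it is meant to remove. Dropping the components from a factor list corrects a list that the plan does not contain.

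**Conclusion.** No change to the plan is needed. The false association between initial DAS28 and change is real and large, 38% to 80% instead of 5% for r from 0.8 to 0.5, but it arises only if an analyst runs that correlation and reads it as prediction, which the text permits and does not state. The same holds for the components.

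For the remaining factors, raw change-score correlation against baseline adjustment is a fair trade-off. At q = 0.6 the raw method's false-positive rate reaches 35% under one model, and the adjusted method's reaches 64% under the other. The Protocol gives no basis for choosing, and all these rates rest on assumed r and q and on equal variances.

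What is left is missing detail on which variables count as factors. An analyst would sensibly leave the score's own parts out and would not read initial level against change as response. This detail may also sit in a separate SAP. The analysis is secondary and worded as exploration, and the primary before-after comparison is untouched.
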